6.2.4 Treatment Planning

Three-dimensional coplanar or non-coplanar beam arrangements will be custom designed for each case to deliver highly conformal prescription dose distributions. Non-opposing, noncoplanar beams are preferable. Typically, ≥ 10 beams of radiation will be used with roughly equal weighting. Generally, more beams are used for larger lesion sizes. When static beams are used, a minimum of 7 non-opposing beams should be used. For arc rotation techniques, a minimum of 340 degrees (cumulative for all beams) should be utilized. For arc rotation techniques, a minimum of 340 degrees (cumulative for all beams) should be utilized. In order to obtain acceptable coverage, field aperture size and shape should correspond nearly identically to the projection of the PTV along a beam's eye view (i.e., no additional "margin" for dose buildup at the edges of the blocks or MLC jaws beyond the PTV). The only exception should be when observing the minimum field dimension of 3.5 cm when treating small lesions (see above). As such, prescription lines covering the PTV will typically be the 60-90% line (where the maximum dose is 100%); however, higher isodoses (hotspots) must be manipulated to occur within the target and not in adjacent normal tissue. The treatment isocenter or setup point in stereotactic coordinates will be determined from system fiducials (and can be adjusted pre-treatment depending on the results from localization imaging studies) and translated to the treatment record.

CONFIDENTIAL

This material is the property of the study sponsor. Do not disclose or use except as authorized in writing by the study sponsor

Printed on 1/31/2017

Dose specifications: Successful treatment planning will require accomplishment of **all** of the following criteria:

1. **Maximum dose:** The treatment plan should be created such that 100% corresponds to the maximum dose delivered to the patient. This point must exist within the PTV.
2. **Prescription isodose:** The prescription isodose surface must be $\geq 60\%$ and $< 90\%$ of the maximum dose.
3. **Prescription Isodose Surface Coverage:** The prescription isodose surface will be chosen such that 95% of the target volume (PTV) is conformally covered by the prescription isodose surface (PTV V95%RX = 100%) and 99% of the target volume (PTV) receives a minimum of 90% of the prescription dose (PTV V90%RX $> 99\%$).
4. **High Dose Spillage:** The cumulative volume of all tissue outside the PTV receiving a dose $> 105\%$ of prescription dose should be no more than 15% of the PTV volume. Conformality of PTV coverage will be judged such that the ratio of the volume of the prescription isodose meeting criteria 1 through 4 to the volume of the PTV is ideally < 1.2 (see table below). These criteria will not be required to be met in treating very small tumors (< 2.5 cm axial GTV dimension or < 1.5 cm craniocaudal GTV dimension) in which the required minimum field size of 3.5 cm (see Section 6.2) results in the inability to meet a conformality ratio of 1.2. The "None" and "Minor" entries in this table define the Per Protocol, Variation Acceptable and Deviation Unacceptable Compliance Criteria (see Section 6.7).
5. **Intermediate Dose Spillage:** The falloff gradient beyond the PTV extending into normal tissue structures must be rapid in all directions and meet the following criteria:
 - a. *Location:* The maximum total dose over all fractions in Gray (Gy) to any point 2 cm or greater away from the PTV in any direction must be no greater than D2CM where D2CM is given by the table below.
 - b. *Volume:* The ratio of the volume of the 34 or 12 Gy isodose volume to the volume of the PTV must be no greater than R50% where R50% is given by the table below (adapted from RTOG 0915). This table is used for all prescription requirements in Section 6.2.4 irrespective of calculation algorithm and total treatment dose.

CONFIDENTIAL

This material is the property of the study sponsor. Do not disclose or use except as authorized in writing by the study sponsor

Printed on 1/31/2017

Table 1: Conformality of Prescribed Dose for Calculations Based on Deposition of Photon Beam Energy in Heterogeneous Tissue

PTV Volume (cc)	Ratio of Prescription Isodose Volume to the PTV Volume		Ratio of 50% Prescription Isodose Volume to the PTV Volume, R _{50%}		Maximum Dose (in % of dose prescribed) @ 2 cm from PTV in Any Direction, D _{2cm} (Gy)	
	Deviation		Deviation		Deviation	
	None	Minor	None	Minor	None	Minor
1.8	<1.2	<1.5	<5.9	<7.5	<50.0	<57.0
3.8	<1.2	<1.5	<5.5	<6.5	<50.0	<57.0
7.4	<1.2	<1.5	<5.1	<6.0	<50.0	<58.0
13.2	<1.2	<1.5	<4.7	<5.8	<50.0	<58.0
22.0	<1.2	<1.5	<4.5	<5.5	<54.0	<63.0
34.0	<1.2	<1.5	<4.3	<5.3	<58.0	<68.0
50.0	<1.2	<1.5	<4.0	<5.0	<62.0	<77.0
70.0	<1.2	<1.5	<3.5	<4.8	<66.0	<86.0
95.0	<1.2	<1.5	<3.3	<4.4	<70.0	<89.0
126.0	<1.2	<1.5	<3.1	<4.0	<73.0	>91.0
163.0	<1.2	<1.5	<2.9	<3.7	<77.0	>94.0

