6.2.3 Dose fractionation and specification

The prescription dose per fraction to the PTV will be 8 Gy per fraction for a bone or lung index lesion and 6Gy per fraction for any liver or subcutaneous index lesion.

The total dose for dose level 1 (our starting dose level) will be one will be 24Gy over 3 fractions for a bone or lung index lesion and 18Gy over three fractions for any liver or subcutaneous index lesion.

If we encounter a dose limiting toxicity, we will then reduce our total dose to dose level -1. The total dose for dose level -1 will be 16Gy over 2 fractions for a bone or lung index lesion and 12Gy over two fractions for any liver or subcutaneous index lesion.

Dose rate: For the purpose of this study, dose rate utilized will be that which is commissioned by the manufacturer and the medical physics group for external beam radiotherapy delivery by the University of Washington Department of Radiation Oncology. There will be no special dose rate modifications required for this study.

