8.4.1 Escalation Design

CONFIDENTIAL

This material is the property of the study sponsor. Do not disclose or use except as authorized in writing by the study sponsor

Printed on 1/31/2017

Because of the successful outcome with 2 and 3 fractions of SBRT in the University of Pennsylvania Phase 1 trial, the initial dose level in this study will be Dose level 1 (3 fractions of SBRT).

Dose level 1. This trial will begin enrolling at dose level 1, 3 fractions of SBRT, which has been shown to be safe in the Phase 1 trial at University of Pennsylvania. However, if one DLT has been observed in any patient, then all remaining patients must be followed for 30 days after the 4th or final injection. Two or more DLTs will cause de-escalation to Dose level -1, which will be the MTD.

Dose level -1. If two or more DLTs are observed in Dose Level 1, then all subsequent patients will be treated at Dose Level -1. If DLTs are observed at dose level -1, this will cause termination of the study.

Replacement of patients: Subjects/patients who discontinue from the study for reasons unrelated to the study (e.g. personal reasons or adverse events after registration but prior to receiving study therapy) may be replaced as required for the study to meet its objectives. Patients that have received study therapy, but who withdraw for reasons unrelated to toxicity prior to the required observation period to determine absence of DLT, will not count toward dose escalation rules and may be replaced as required. The decision to remove a subject/patient and to replace dropouts will be made by the principal investigator. The replacement will receive the same treatment or treatment sequence (as appropriate) as the allocation number replaced.

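### Criterion 5b names a 34 or 12 Gy isodose for the R50% test; 12 Gy is half of only the 24 Gy prescription and 34 Gy is half of none, so the literal test is too lenient for the 18 Gy liver/subcutaneous stratum

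*Combined protocol and SAP*

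**What the plan says.** Section 6.2.3 sets the starting dose at "24Gy over 3 fractions for a bone or lung index lesion and 18Gy over three fractions for any liver or subcutaneous index lesion", and dose level -1 at "16Gy over 2 fractions for a bone or lung index lesion and 12Gy over two fractions for any liver or subcutaneous index lesion". Section 8.4.1 confirms that "the initial dose level in this study will be Dose level 1 (3 fractions of SBRT"), so 24 and 18 Gy are the prescriptions in force from the first patient.

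Section 6.2.4 lists plan-acceptance criteria, all of which must be met. Criterion 5b requires that "The ratio of the volume of the 34 or 12 Gy isodose volume to the volume of the PTV" stay within R50% as tabulated. It does not say which of the two doses belongs to which stratum. The Table 1 column for R50% is headed "Ratio of 50% Prescription Isodose Volume to the PTV Volume", and the text before the table adds: "This table is used for all prescription requirements in Section 6.2.4 irrespective of calculation algorithm and total treatment dose".

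Criterion 3, on target coverage, asks that "95% of the target volume (PTV) is conformally covered by the prescription isodose surface (PTV V95%RX = 100"%), together with a second condition that 99% of the PTV receive at least 90% of the prescription, abbreviated as V90%RX > 99%.

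**The concern.** R50% is a relative quantity: the volume enclosed by half the prescription dose, divided by the PTV volume. A fixed dose in Gy can stand in for it only when that dose is half the prescription. Criterion 5b gives two fixed doses for a protocol with four prescriptions, and at most one of the pairings can be right.

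5b is the only volume limit on intermediate-dose spill. If the tested isodose is above half the prescription, the measured volume is too small and a plan can pass with more normal tissue irradiated than Table 1 intends. Radiation-related toxicity is what triggers de-escalation here, so a plan-acceptance rule that errs in this direction deserves correction even though no statistical quantity depends on it.

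The criterion 3 bracket is a separate slip. It concerns dose to the target, not to normal tissue.

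**Working it through.** **Inputs.** Prescriptions of 24, 18, 16 and 12 Gy (section 6.2.3). Isodoses of 34 and 12 Gy (criterion 5b). R50% limits from 5.9 at 1.8 cc down to 2.9 at 163 cc (Table 1). Prescription isodose at least 60% of maximum (criterion 2). Tissue outside the PTV above 105% "of prescription dose should be no more than 15% of the PTV volume" (criterion 4).

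**Step 1: which isodose is the 50% isodose?** Half-dose = Rx/2; named dose as a share of prescription = 12/Rx and 34/Rx; highest permitted point dose = Rx/0.60.

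| Prescription | Level, site | Rx/2 | 12 Gy as % of Rx | 34 Gy as % of Rx | Highest point dose |
|---|---|---|---|---|---|
| 24 Gy | 1, bone/lung | 12 Gy | 50% | 142% | 40 Gy |
| 18 Gy | 1, liver/subcutaneous | 9 Gy | 67% | 189% | 30 Gy |
| 16 Gy | -1, bone/lung | 8 Gy | 75% | 213% | 26.7 Gy |
| 12 Gy | -1, liver/subcutaneous | 6 Gy | 100% | 283% | 20 Gy |

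The plan's 12 Gy is reproduced only for 24 Gy. Its 34 Gy would need a 68 Gy prescription, which the protocol does not use.

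**Step 2: direction of the error.** Isodose volumes are nested: V(12 Gy) ≤ V(9 Gy). For the 18 Gy prescription the ratio tested can therefore never exceed the true R50%. This needs no assumption about fall-off.

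**Step 3: the 34 Gy reading.** For 18, 16 and 12 Gy the highest permitted point dose is below 34 Gy, so the volume is zero and the test always passes. For 24 Gy, 34 Gy exceeds 105% of prescription (1.05 × 24 = 25.2 Gy), so criterion 4 gives V(34 Gy) ≤ PTV + 0.15 PTV = 1.15 PTV. That is below the smallest R50% limit of 2.9, so again the test cannot fail, except for very small tumors exempted from the criteria.

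**Step 4: the 12 Gy reading for a 12 Gy prescription (level -1 only).** The tested volume is the prescription isodose volume, which Table 1 already holds below 1.2 × PTV (minor deviation 1.5). Limits of 2.9 to 5.9 add nothing, with the same small-tumor caveat.

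**Step 5: illustrative size for 18 Gy.** Take a 34 cc PTV (limit 4.3, minor limit 5.3) and a plan exactly at the limit when tested at 12 Gy, so V(67%)/PTV = 4.3. Assume V(100%)/PTV = 1.2. From 100% to 50% of prescription is 1.5 times the step from 100% to 67%. The fall-off shape is an assumption; three choices give:

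- Volume linear in dose: 1.2 + 1.5 × (4.3 − 1.2) = 5.85.
- Equivalent-sphere radius linear in dose: cube roots 1.063 and 1.626, so (1.063 + 1.5 × 0.563)³ ≈ 6.9.
- Log volume linear in dose: 4.3^1.5 / 1.2^0.5 = 8.14.

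All three exceed the minor limit of 5.3. With the radius model, the true R50% at PTVs of 1.8, 7.4, 22, 50 and 163 cc is 10.4, 8.6, 7.4, 6.3 and 4.2, against minor limits of 7.5, 6.0, 5.5, 5.0 and 3.7.

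**Step 6: criterion 3.** In the second condition the subscript is the dose and the right-hand side is the volume. On that notation the first bracket means 95% of prescription to all of the PTV, whereas the words mean 100% of prescription to 95% of it.

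| Rx | Words, first condition | Bracket, first condition | Second condition |
|---|---|---|---|
| 18 Gy | 18 Gy to 95% | 17.1 Gy to 100% | 16.2 Gy to 99% |
| 24 Gy | 24 Gy to 95% | 22.8 Gy to 100% | 21.6 Gy to 99% |

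The bracket makes the second condition redundant: if all of the PTV receives 95% of prescription, more than 99% of it receives 90%. The words do not.

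**The case against.** The strongest reply is that the plan already holds the right definition. 5b calls its limit R50% and sends the reader to Table 1, whose heading specifies the half-prescription isodose. Criterion 4 says that the table's None and Minor entries define the compliance categories. Since 5b assigns neither dose to a stratum, it cannot be applied alone. A planner who finds 34 Gy impossible for an 18 Gy plan would probably take it for a leftover figure and use 9 Gy. This stands as mitigation, and it is why no claim is made that any plan was wrongly accepted. It does not remove the contradiction: 12 Gy is a plausible dose in an 18 Gy plan and would not stand out as an error.

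Other criteria also restrain spill, but incompletely. The prescription-isodose ratio of 1.2 is worded as an ideal, criterion 4 as a recommendation, and very small tumors can be exempt (lesions from 1 cm are eligible). The D2cm limit does not replace R50%, even read as a percentage of prescription as its heading says. For a spherical 13.2 cc PTV (radius 1.47 cm), a 50% limit at 2 cm only confines the half-dose volume to (3.47/1.47)³ ≈ 13 times the PTV, against an R50% limit of 4.7.

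It is also fair that Step 5 rests on a plan placed exactly at the limit and on assumed fall-off. The documents establish the direction of the error, not its size. The level -1 mismatches arise only after de-escalation. Finally, criterion 3 is a different matter and adds no weight to the point about 5b; it is included because it sits in the same list and can be corrected in the same edit.

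**Conclusion.** The concern holds. As written, 5b is correct for one of four prescriptions if 12 Gy is used, and for none if 34 Gy is used. In the liver/subcutaneous stratum, planned at 20 of the 40 patients, the mismatch is present from the starting dose: 12 Gy is 67% of prescription where 50% is meant. Every mismatch errs towards accepting more intermediate dose in normal tissue; that follows from nesting alone. The illustrated R50% of about 5.9 to 8.1 against a limit of 4.3 depends on the assumed fall-off and prescription ratio of 1.2.

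The correction should be made, since this is a wrong figure in a mandatory acceptance rule. Its practical effect may be small if planners have followed the Table 1 heading.

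**What to change.** In criterion 5b, replace the two fixed doses with the 50% prescription isodose volume, and list the values: 12 Gy for 24 Gy, 9 Gy for 18 Gy, 8 Gy for 16 Gy, 6 Gy for 12 Gy. In criterion 3, change the first bracket to PTV V100%RX = 95%, which matches its words and keeps the second condition meaningful. The physics investigators should confirm both.

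The cost is two wording edits, with the usual notification of a protocol change to the IRB. Only accepted plans tested at 34 Gy, or at 12 Gy for a prescription other than 24 Gy, need rechecking. Where the tested isodose was not recorded, it would have to be established from the plan.

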6.3 Ipilimumab Administration

Ipilimumab will be given in the outpatient setting. Patients will receive ipilimumab at 3 mg/kg i.v. delivered as per the package insert every 3 weeks (+/- 2 days) for treatments. Patients will be monitored in the clinic after the infusion and discharged when deemed stable by the clinical staff. Medications to treat hypersensitivity reactions should be immediately available, and may include epinephrine, diphenhydramine, methylprednisolone and nebulized albuterol.

6.4 Study Visit Schedule

After the subject consents and is deemed eligible for the study baseline imaging appropriate for RECIST criteria will be obtained (if not previously done or it has been greater than 60 days since the last scan) and a blood draw for purpose of immunological studies will be drawn. Baseline and post-treatment imaging will be evaluated by immune-related Response Evaluation Criteria in Solid Tumors (RECIST) version 1.1. This will be referred to as irRECIST 1.1 criteria described in section 7.1.1. Subjects will then be seen in the outpatient clinics to assess treatment-related toxicities once during radiation treatment. At this visit, a history and targeted physical examination will be performed.

During ipilimumab administration following radiotherapy, subjects will be evaluated by one of the investigators or their designated nurse practitioner at the time of each infusion. A history and directed physical examination will be performed.

6.5 Study Calendar

	Eligibility/Pre-Treatment	Post-SBRT; Pre- Ipi	Ipilimumab Clinic Visits	EOS visit
Tests and Observations				
History and PE	X		X	X(as per

CONFIDENTIAL

This material is the property of the study sponsor. Do not disclose or use except as authorized in writing by the study sponsor

Printed on 1/31/2017

				standard of care, usually within 60 days of final ipilimumab infusion)
ECOG score	X		X	X
Radiographic imaging appropriate for ir-RECIST 1.1 criteria (should be the same modality at baseline and EOS) ^b	X			X(as per standard of care, usually within 60 days of final ipilimumab infusion)
Biopsy	X			X ^C
Laboratory				
CBC w/diff, Hgb, Platelets... ^b	X	X ^d	X ^d	
CMP ^b	X	X ^d	X ^d	
Pregnancy Test	X ^a			
Toxicity Assessment	X	X	X	X
Immune studies (Eight 8.5 ml yellow top tubes and one 10 ml SST tube)	X	X ^d	X ^d	x

X^a- Required for women of childbearing potential. If pre-treatment is 30 days from eligibility, you should repeat a pregnancy test within 24 hours of treatment initiation.

X^b- Measurements cannot be more than 60 days from the beginning of treatment.

X^C- As clinically indicated, tumor blocks and/or slides from EOS biopsy or surgery will be collected on all patients.

X^d- The post-SBRT; pre-Ipi Ipilimumab #1 Immune studies and routine clinic blood draw may be combined if last SBRT and the first injection of Ipilimumab will occur within 5 days of each other.

6.6 Post-treatment Evaluation and follow-up

Patients will be evaluated per standard of care, usually within 60 days after last ipilimumab treatment (End of Study visit, EOS) to determine feasibility and safety (acute toxicity) for the initial phase of the study. Follow-up imaging appropriate for ir-RECIST 1.1 criteria will be obtained within 60 days of the final dose of ipilimumab for restaging. The same imaging modality should be used at follow-up as at baseline. Specimens for immune correlates will also be drawn at this visit. Patients will then be referred to the referring physician for subsequent follow up, according to standard of care. Every effort will be made to obtain records of patients during this follow up, and permission will be sought for the investigators and/or study team to re-contact the patient directly with regard to health status and toxicity.

CONFIDENTIAL

This material is the property of the study sponsor. Do not disclose or use except as authorized in writing by the study sponsor

Printed on 1/31/2017

7 Assessment of Tumor Response

7.1.1 Tumor Response (Immune-related response criteria)

Overall clinical response which will be assessed by Response Evaluation Criteria in Solid Tumors (RECIST) version 1.1, using primarily CT scans, immune response criteria and/or clinical benefit as assessed by the investigator). This will be referred to as irRECIST

7.1.2 1.1. Immunological Outcome Assessment

Blood samples from patients for immune studies will be obtained as in the Schedule of Activities table for assays such as those noted below. The extent of immune assessment will depend on availability of cells or serum.

Analysis of antigen presenting cell (APC) activation. For this assay, peripheral blood lymphocytes are analyzed for evidence of APC activation. Using unmanipulated peripheral blood, B cells and dendritic cells before and after treatment can be analyzed using flow cytometry to measure cell surface immune markers using a panel of immune parameters such as CD19, CD123, CD11c (to define the subsets) and CD86, MHC class I and II, CD70, and CD54 to measure activation. Dead cells are excluded using 7-AAD and non-B cells or non-DC are excluded using a panel of mAb, all analyzed on a “dump” channel. For each parameter and each APC, the percentage of cells positive for the marker and/or MFI at time points after CP-870,893 infusion are compared to baseline and the change are calculated as $\%_{\text{after}}/\%_{\text{baseline}}$ or $\text{MFI}_{\text{after}}/\text{MFI}_{\text{baseline}}$.

Analysis of T cell activation. Three main assays are available to assess T cells before and after treatment:

1. Multi-parameter flow cytometry. Together with complete blood count differentials, flow cytometry are used to measure both the percentages and absolute count (cells/mm³) of important T cell subsets defined by immunophenotyping, such as total CD3+ cells, CD3+ CD8+ T cells, CD3+ CD4+ T cells, and CD3+ CD4+ Foxp3+ regulatory T cells. For each subset, differentiation status (e.g. naïve, central memory, effector memory) or activation status are assessed using additional markers such as CD45RA, CD45RO, CCR7, CD28, CD27, CD57, CD25, CD69, HLA-DR, CTLA4, and PD-1. When possible, trends can be tracked in T cell subsets based on analysis of multiple post-treatment samples. NK cells subsets can also be assessed using CD16 and CD56, with CD69 as an activation marker.

2. Antigen-specific T cell assays. To determine if treatment is associated with the induction of tumor antigen-specific CD8+ T cell responses, a series of assays to measure specific T cell responses, comparing pre and post treatment samples, are available. The immune assessment approach employed depends in large part on the patient's HLA type. Priority will be placed on assessment of specific T cells after one round of in vitro stimulation. For patients expressing common HLA alleles such as HLA-A2, in vitro stimulation of peripheral T cells can be performed using peptides derived from melanoma antigens known to bind to HLA alleles that match the patient. For HLA-A2 patients, specific T cell induction can be enumerated with peptide/HLA-A2 tetramers and function can be measured by intracellular IFN-gamma production in response to peptide loaded T2 cells. For non-HLA-A2 patients, T cell response can be measured using peptide-loaded autologous PHA blasts.

3. Tumor-specific T cell assays. For patients of any HLA type, tumor-specific responses can be measured using RNA loaded APC for in vitro stimulation of patient T cells. In this approach, CD40-activated B cells are generated from patient baseline samples, electroporated

CONFIDENTIAL

This material is the property of the study sponsor. Do not disclose or use except as authorized in writing by the study sponsor

Printed on 1/31/2017

with either total tumor RNA pooled from allogeneic melanoma cell lines or autologous total tumor RNA (when available) vs. GFP mRNA as a control. After 7 days in culture, stimulated autologous T cells can be scrutinized for responses specific for intracellular IFN-gamma response to autologous PHA blasts electroporated with tumor RNA vs. GFP mRNA.

Serum cytokine analysis. For this assay, serum can be used to determine concentrations of cytokines including IL-1, TNF-alpha, IL-6 and others using Luminex or Cytokine Bead Array platforms.

Specimens collected at the University of Washington and Seattle Cancer Center will be de-identified, frozen, and analyzed at the end of the study.

As research collaborations are developed with other immunology laboratories, de-identified specimens may be sent to labs for additional immunological testing. In addition, some specimens may be retained at the University of Washington for future, immunological research.

8 Statistical Plan

